Specific Aim 2: To determine the incidence of developing a septic arthritis in patients with a non-operatively treated traumatic arthrotomy.

Hypothesis 2: Non-operative treatment of small traumatic arthrotomies will have an extremely low rate (<10%) of subsequent septic arthritis over a 3-month period.

Specific Aim 3: To determine the incidence of developing a septic arthritis in patients with operative treatment of a traumatic arthrotomy.

Hypothesis 3: Operative treatment of traumatic arthrotomies will have an extremely low rate (<5%) of subsequent septic arthritis over a 3-month period.

Specific Aim 4: To determine the need for additional surgery (ex: foreign body removal) in patients with a non-operatively treated traumatic arthrotomy.

Hypothesis 4: Non-operative treatment of small traumatic arthrotomies will have an extremely low rate subsequent surgery over a 6-month period.

Specific Aim 5: To provide a description of traumatic arthrotomies successfully treated non-operatively.

Hypothesis 5: Arthrotomies will be less than 1 cm with a soft tissue injury amenable to closure in the ED. Arthrotomies will be more likely to be due to GSW's and scraping mechanisms rather than direct penetration.

Study Design

Prospective Multi-center Observational Cohort
Retrospective chart review

Study Population

Inclusion Criteria

1. Any patient 18 and older with a traumatic arthrotomy (of any major joint) confirmed by saline load test, direct visualization of a capsular rent or intra-articular contents, or air in the joint on CT or radiographs.
 - a. Major Joints Include:
 - i. Knee
 - ii. Elbow
 - iii. Wrist
 - iv. Shoulder
 - v. Hip
 - vi. Ankle

Exclusion Criteria

1. Patients who will have severe problems with maintaining follow-up

Method for Selecting Samples

Potential patients will be prospectively identified at the time of the initial consultation or at the first clinic follow-up appointment based on the diagnosis of a traumatic arthrotomy (Diagnostic criteria noted in inclusion criteria above).

Patients will be screened by their inclusion and exclusion criteria, and if met will be considered for enrollment in the study.

Retrospective chart review

The study will also conduct a retrospective chart review of patients who presented with a traumatic arthrotomy during the enrollment period, however were unable to be reached for consent after multiple attempts over a period of two years.

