Information about injury and treatment outcomes will be collected from the medical record.

Representativeness of the Sample

The study population will be representative of the typical trauma population.

Patients of all ages, genders, ethnicities, and backgrounds will be included in this study. Based on previous clinical series of patients at our institution, we expect that 70% of our patients will be men and 25% minority patients.

Definition of Variables

Outcome Variables

- Primary Outcomes
 - Cost of treatment
 - Adverse Events
 - Development of septic arthritis
 - Return to operating room for any reason (ie: foreign body removal)
 - Rehospitalization
 - Development of osteomyelitis
- Secondary Outcomes
 - Superficial wound infection
 - Extra-articular infection requiring a prolonged course of antibiotics or local wound care.
 - Pain 1 – 10 Scale
 - Current
 - Worst in last 24 hours
 - At rest
 - Bearing weight
 - Ambulating
 - Return to work or previous level of activity

Demographic Variables and Covariates

- Demographic Information

- Age
- Gender
- BMI
- Mechanism of injury
- Smoking Status
- Comorbidities
- Employment status
- Workers compensation status
- Additional Injuries
- Arthrotomy Characteristics
 - Mechanism of arthrotomy
 - Abrasion
 - Laceration
 - Puncture
 - GSW
 - Blast injury
 - Degree of contamination
 - Size of arthrotomy (mm)
 - Shape of arthrotomy
 - Method of Diagnosis
 - Visualization
 - Air on CT or radiograph
 - Saline load
- Treatment Characteristics
 - Antibiotics administered
 - Timing
 - Duration
 - Indication for Surgery
 - OR for additional injury
 - Intra-articular fracture requiring operative fixation
 - Heavily contaminated
 - Intra-articular loose body
 - Large arthrotomy
 - Intra-articular hardware

Potential Confounders

As a prospective observational study, the patient's treatment will not be altered by their inclusion in the study. No guidelines will be provided to influence the treating surgeons' decision making. All surgeons will have treated patients based on their own expert opinion and biases, which will undoubtedly differ between surgeons. The purpose of the study is to show that some traumatic arthrotomies can be treated non-operatively based on surgeon discretion, and having a variety of different arthrotomies will add to the descriptive nature of the study.

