The observational nature of this study will introduce a selection bias based on the surgeon's comfort level of treating traumatic arthrotomies non-operatively. Larger and more heavily contaminated arthrotomies will be far more likely to be treated operatively compared to smaller, less contaminated arthrotomies. Any comparisons made between operative and non-operative treatment will have to be made between a matched cohort of arthrotomies of similar severity.

Although the treatment of patients should not be altered by their inclusion in the study, the possibility of a Hawthorne (observer) effect bias exists. The treating surgeon's decision making may potentially be altered by participation in this study.

Patient Safety

Patients involved in the study will not have their medical care altered in any way by their participation. A data safety monitor will be appointed to periodically assess for adverse events. .

Methods

Patient Identification and Enrollment

Patients will be identified at the time of the initial consultation or first clinic follow-up visit based on the presence of a traumatic arthrotomy, of any major joint, based on the criteria outlined above. Patients meeting the inclusion and exclusion criteria will be deemed eligible for the study. Eligible patients will be approached by a member of the treatment team to further discuss the study. If the patient agrees, a member of the research staff will discuss the study in greater detail and obtain informed consent.

Intervention

There will be no alterations in patient care by their inclusion in the study. The attending surgeon will determine the treatment plan, follow-up frequency, and follow-up duration. The need for additional surgery will also be determined by the attending surgeon. The development of septic arthritis or need to proceed to the operating room for foreign body removal will be deemed as adverse events and will be reported to the data safety monitor as they occur.

Data Collection

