At the initial consultation, patient demographic information, arthrotomy characteristics, treatment variables, and additional injuries will be obtained. At each follow-up appointments, pain level will be assessed by a member of the treatment team and recorded. Patient will complete the VR-12 to assess quality of health at 3 month after time of their injury. Patients may be followed prospectively for a total of one year after the time of their injury. Patients released from care prior to their one year appointment will be contacted via telephone by a member of the research staff to assess final outcomes. The total cost of care, including hospital and office charges, will be recorded at the one year mark. Patients still requiring care at the 3 month visit as a direct result of treatment of their traumatic arthrotomy will continue to be followed for a total of one year.

Follow-Up

A minimum necessary follow-up of 3 months or 1 year for patient requiring care as a direct result of treatment of their traumatic arthrotomy. Patients released from care after this time period without developing septic arthritis will be considered a successful therapy. If a patient is discharged from clinic prior to 3 months or 1 year, a member of the research team will contact the patient by telephone or by mail to obtain final follow up information.

Data Collection

All data will be entered into REDCap, a web-based data entry and management system that provides logic checks on input and checks for invalid entries. Data will be entered continuously as they are collected and stored in univariate form. We will also run standard checks for outliers, duplicates and other types of errors which may occur within a complex data file. All data files will be password protected and hard copies of blinded patient records will be maintained in locked cabinets in the research office.

Study Duration

Patients will continue to be enrolled for 2-years or until 25 patients are treated non-operatively, whichever comes first.

Statistical Analysis

Standard statistical tests will be used. Descriptive statistics including means and standard deviations, or counts and percentages will be reported. The principal analysis will compare cost of care using logistic regression. Also, demographic and baseline variables will be compared between operative and non-operative patients using t-test and chi-square test where applicable.

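### The only success rule counts septic arthritis alone, so Aim 5 could describe some patients with other arthrotomy-related adverse events as non-operative successes

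*Combined protocol and SAP*

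**What the plan says.** The Follow-Up section of the combined protocol and SAP contains the only statement of treatment success: "Patients released from care after this time period without developing septic arthritis will be considered a successful therapy". The period is at least 3 months, or 1 year for patients who still need care because of the arthrotomy. The sentence covers operative and non-operative patients alike and cites no aim.

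Specific Aim 5 is "To provide a description of traumatic arthrotomies successfully treated non-operatively". It has no success rule of its own. Hypothesis 5 proposes a profile by size, closure in the emergency department and mechanism.

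Specific Aim 4 is "To determine the need for additional surgery (ex: foreign body removal) in patients with a non-operatively treated traumatic arthrotomy". Hypothesis 4 expects that such treatment "will have an extremely low rate subsequent surgery over a 6-month period".

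Under Definition of Variables, the primary outcomes include four adverse events: septic arthritis, return to the operating room whatever the reason, rehospitalisation (no cause specified) and "Development of osteomyelitis". The Intervention section pairs septic arthritis with foreign body surgery: "need to proceed to the operating room for foreign body removal will be deemed as adverse events".

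Enrolment runs for 2 years or until 25 patients have been treated non-operatively. A retrospective chart review adds patients who "were unable to be reached for consent after multiple attempts over a period of two years".

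**The concern.** The plan treats four events as primary adverse events, but its success rule looks at only one of them. A patient can therefore be an adverse event in one section and a success in another.

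This matters for Aim 5, where the study says which arthrotomies did well without surgery. The Potential Confounders section gives the study's purpose as showing that some of these injuries can be managed that way at the surgeon's discretion. A patient readmitted for the injury, or treated for osteomyelitis, does not illustrate that. If such patients enter the success group, their wound size, contamination and mechanism become part of the profile that readers may use to select patients for non-operative care.

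The time windows also differ. A patient who needs no further care can be a success at 3 months, while Hypothesis 4 counts surgery over 6 months.

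**Working it through.** The plan gives no figure for this point, so there is nothing to reproduce. The check compares the sections and then gives a scale.

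**Step 1. Treatment of each event.**

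| Event | Primary Outcomes | Intervention | Follow-Up success rule |
|---|---|---|---|
| Septic arthritis | adverse event | adverse event | prevents success |
| Return to the operating room | adverse event | adverse event (foreign body removal) | not mentioned |
| Rehospitalisation | adverse event | not mentioned | not mentioned |
| Osteomyelitis | adverse event | not mentioned | not mentioned |

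**Step 2. Three hypothetical non-operative patients, none with septic arthritis, all eventually released.**
- Readmitted because of the arthrotomy, no operation: meets the success rule.
- Treated for osteomyelitis, no joint operation: meets the success rule.
- Foreign body removed in the operating room at 2 months: meets the success rule. Whether this patient belongs in Aim 5 depends on what non-operative means there. Aim 4 applies the term to patients who then need surgery. On that usage the patient is included; on a narrower reading of Aim 5 the patient is not.

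The requirement to be released delays success for patients still under care at 3 months. It does not exclude them once they are released.

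**Step 3. How many patients.** The only input from the documents is n = 25, the enrolment cap for non-operative patients; chart-review patients could add to it. The event rates r are assumptions. n = 15 shows the case where 2 years pass before the cap is reached. Expected number = n × r. Chance of at least one = 1 − (1 − r)^n.

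| Reading | r | Expected, n = 25 | At least one, n = 25 | At least one, n = 15 |
|---|---|---|---|---|
| Narrower: rehospitalisation or osteomyelitis only | 1% | 0.25 | 22% | 14% |
| | 2% | 0.5 | 40% | 26% |
| | 4% | 1 | 64% | 46% |
| Aim 4 usage: later joint surgery as well | 2% | 0.5 | 40% | 26% |
| | 4% | 1 | 64% | 46% |
| | 8% | 2 | 88% | 71% |

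Worked example: r = 4%, n = 25 gives 1 − 0.96^25 = 0.640.

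**Step 4. Effect on the description.** Assume a feature present in 12 of 25 described successes (48.0%). Remove k wrongly included patients. If all have the feature, the proportion is (12 − k)/(25 − k); if none has it, 12/(25 − k).
- k = 1: 11/24 = 45.8% to 12/24 = 50.0%
- k = 2: 10/23 = 43.5% to 12/23 = 52.2%
- k = 3: 9/22 = 40.9% to 12/22 = 54.5%

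The shift is about 2 percentage points for one patient and up to about 7 for three. For comparison, the standard error of 12/25 is √(0.48 × 0.52/25) = 0.100, or 10 points.

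**The case against.** The link to Aim 5 is inferred. The success sentence sits under Follow-Up, covers both groups and names no aim. That is correct. But no other definition exists, so if this one does not govern Aim 5, the aim has no rule and needs the same sentence.

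The ordinary sense of Aim 5 arguably excludes anyone later operated on for the arthrotomy. Aim 4 has to label patients by initial treatment in order to count later surgery, and it does not speak of success. This is a fair reading, so the joint-surgery part of the point is conditional. A reader might infer that the plan plainly counts patients who later had joint surgery as non-operative successes; the documents leave that open. The narrower reading does not deal with rehospitalisation or osteomyelitis.

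Success based on septic arthritis is a coherent choice, since the Background presents debridement as a means of preventing it. This stands for Aims 2 and 3, whose rates should stay as they are. It is weaker for Aim 5, because the plan itself calls the other events adverse.

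A reader might also infer that failures are hidden or that the main results are biased. The documents do not support this. Each event is a primary outcome, additional surgery has its own aim, and septic arthritis and foreign body surgery go to the data safety monitor. The Statistical Analysis section specifies no test on the success label. No direction of bias in the described features can be derived.

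**Conclusion.** The point holds in a limited form. Under the only stated success rule, a non-operative patient with an arthrotomy-related rehospitalisation or osteomyelitis can be described under Aim 5 as a success. A patient with a later unplanned joint operation can be as well, if Aim 4's usage applies. This is an inconsistency between a stated rule and the plan's own list of adverse events, not merely missing detail.

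The effect is minor: about 2 percentage points per misclassified patient out of 25, and even three such patients shift the assumed feature by less than one standard error. The septic arthritis, reoperation and cost results are unaffected. The conclusion rests on reading the Follow-Up rule into Aim 5. The event rates and the 12-of-25 feature are assumptions, and the restriction to arthrotomy-related rehospitalisation is this review's, since the plan states no cause.

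A reader might infer from Hypothesis 4 that success can simply be assessed at 6 months for everyone. The plan does not assure this: minimum follow-up is 3 months, and no date is fixed for the telephone contact.

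**What to change.** Add to the Follow-Up section, for Aim 5 only: success is release from care with no septic arthritis, osteomyelitis, unplanned operation on the injured joint or arthrotomy-related rehospitalisation recorded through the patient's last planned contact. Surgery planned at presentation for other injuries is not a failure.

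Use a 6-month window only where the medical record, or the telephone contact already planned for patients released before one year, reaches 6 months. Otherwise report status as unknown beyond the last contact.

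In Aim 5, describe successes and failures side by side. Keep the septic-arthritis-only rates for Aims 2 and 3, and keep return to the operating room from any cause as a separate outcome.

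The change is to wording and uses events already collected, with no added visit or questionnaire. Its costs are a slightly smaller success group (for example 23 instead of 25), a judgement on whether each rehospitalisation was arthrotomy-related, and an unknown-status category. Chart-review patients, who could not be reached, will often fall into that category if their record ends early. Requiring 6-month status for everyone could need a later call, so that is not proposed.

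### With at most 25 prospective non-operative patients and no interval named, an observed septic arthritis rate below 10% would not by itself establish Hypothesis 2

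*Combined protocol and SAP*

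**What the plan says.** Specific Aim 2 is worded as estimation: "To determine the incidence of developing a septic arthritis in patients with a non-operatively treated traumatic arthrotomy". Hypothesis 2 then attaches a number: "Non-operative treatment of small traumatic arthrotomies will have an extremely low rate (<10%) of subsequent septic arthritis over a 3-month period". Under Outcome Variables, "Development of septic arthritis" is among the primary outcomes.

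Study Duration limits prospective recruitment: "Patients will continue to be enrolled for 2-years or until 25 patients are treated non-operatively, whichever comes first". So 25 is a ceiling, and fewer are possible. No precision, power or assumed event rate is given for it.

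For rates, Statistical Analysis offers "Descriptive statistics including means and standard deviations, or counts and percentages will be reported". It also says "Standard statistical tests will be used", without naming one for Hypothesis 2. The t-test and chi-square test are assigned to demographic and baseline comparisons and logistic regression to cost; a further regression looks for predictors of poorer outcomes. Significance is set at 0.05, with sidedness not stated. No confidence interval and no comparison with 10% appears.

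On who is counted, Follow-Up sets a 3-month minimum (1 year if care is still needed), counts release without septic arthritis as success, and provides telephone or mail contact after early discharge. The only exclusion criterion is expected severe difficulty with follow-up. A retrospective chart review covers patients who could not be reached for consent.

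**The concern.** A numeric threshold on a primary safety outcome has no stated way of being judged. In 25 patients, 0, 1 or 2 infections (0%, 4% or 8%) all look as if they meet the threshold, although each is compatible with a true rate above 10% on an exact interval. Readers could come away believing that a rate below 10% has been shown.

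The denominator is also only partly fixed. The plan does not say how patients whose 3-month outcome stays unknown are counted, or whether chart-review patients are pooled with the prospective cohort. With so few events, settling these points after the data are seen could change the answer. A lesser point is that Aim 2 covers all non-operative arthrotomies while Hypothesis 2 covers small ones. Inclusion has no size limit, and the only size given is a prediction in Hypothesis 5: "Arthrotomies will be less than 1 cm with a soft tissue injury amenable to closure in the ED".

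**Working it through.** **Inputs.** n = 25 at most (Study Duration); threshold 10% at 3 months (Hypothesis 2); significance level 0.05 (Statistical Analysis). The plan gives no derivation of 25, so there is no figure of its own to reproduce.

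**Step 1: which results look favourable.** 2/25 = 8% and 3/25 = 12%, so an observed rate below 10% means 0, 1 or 2 infections.

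**Step 2: exact limits and p-values.** The Clopper-Pearson upper limit is the rate p that solves P(X ≤ x | 25, p) = 0.025 (two-sided 95%) or 0.05 (one-sided 95%). At x = 0 it is 1 − 0.025^(1/25) = 13.7% or 1 − 0.05^(1/25) = 11.3%. The one-sided p-value against 10% is P(X ≤ x | 25, 0.10); at x = 0 it is 0.9^25 = 0.072.

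| Infections | Observed | Two-sided 95% upper limit | One-sided 95% upper limit | One-sided p against 10% |
|---|---|---|---|---|
| 0/25 | 0% | 13.7% | 11.3% | 0.072 |
| 1/25 | 4% | 20.4% | 17.6% | 0.271 |
| 2/25 | 8% | 26.0% | 23.1% | 0.537 |

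No row excludes 10%. With fewer patients the limit rises: 0/20 gives 16.8% two-sided.

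**Step 3: event-free number needed.** Requiring 0.9^n ≤ 0.05 gives n ≥ ln 0.05 / ln 0.9 = 28.4, so 29. Requiring 0.9^n ≤ 0.025 gives n ≥ 35.01, so 36.

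**Step 4: dependence on method.** Upper limits at 0/25 by other methods:
- Below 10%: Wilson one-sided 9.8%; mid-p one-sided 8.8%; Jeffreys 95th and 97.5th percentiles 7.3% and 9.5%.
- Above 10%: Wilson two-sided 13.3%; mid-p two-sided 11.3%.

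At 1/25 the lowest of these methods (Jeffreys 95th percentile) gives 14.6%, so none is below 10%. The choice of method matters only at zero events, but there it decides the answer.

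**Step 5: if an observed rate below 10% were read as confirmation.** P(X ≤ 2 | 25, 0.10) = 0.0718 + 0.1994 + 0.2659 = 0.537. The same probability is 0.41 at a true rate of 12% and 0.25 at 15%. This reading is not a rule in the plan.

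**Step 6: denominator, with assumed numbers.**
- Unknown outcomes: suppose 3 of 25 have no 3-month outcome and the other 22 are infection-free. Leaving the 3 out gives 0/22, upper limit 15.4%. Counting them as uninfected gives 0/25, upper limit 13.7%. Counting them as infected gives 3/25 = 12.0%, upper limit 31.2%. The last is the extreme bound.
- Chart-review patients: adding 11 event-free non-operative patients gives 0/36, two-sided exact limit 9.7%. Adding 4 gives 0/29, one-sided exact limit 9.8%. Pooling could therefore carry the result below the threshold, but infections treated elsewhere may be missing from those records.

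**The case against.** The strongest reply is that this is a descriptive cohort whose principal analysis is cost. Aim 2 asks for an incidence, and Potential Confounders says that "having a variety of different arthrotomies will add to the descriptive nature of the study". A reader might infer that the plan will declare Hypothesis 2 confirmed whenever the observed percentage is below 10%; the documents do not say so. The 54% in Step 5 therefore describes a possible misreading and is not an operating characteristic of the plan. A reader might also infer that 25 is a miscalculated sample size. It is a stopping limit with no calculation behind it, so there is nothing to have miscalculated. Nor would zero infections in 25 be uninformative: p = 0.072 is some evidence, short of 0.05.

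Three further replies stand in part. Counts will be reported, so a reader can compute an interval; but that leaves the method open at 0/25, where it matters. The follow-up exclusion and the telephone or mail contact should keep unknown outcomes few; but there is no rule for those that remain. The chart review could raise the number above 25, so the ceiling applies only to the prospective cohort; but the plan does not say whether the two are combined.

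Clopper-Pearson is a conservative choice, and another interval would be acceptable if named beforehand. For the below-5% expectation in Hypothesis 3 no calculation is possible, because the documents give no operative sample size.

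**Conclusion.** The concern holds in limited form, as something that should be fixed. The plan's stated summary of rates cannot support the below-10% claim from its prospective non-operative cohort under exact methods: even the best possible result, 0/25, leaves a two-sided upper limit of 13.7%. This rests on independent binomial outcomes, at most 25 evaluable prospective patients, and the 0.05 level. It depends on method only at zero events. The gap concerns what may be concluded about the threshold. It does not undermine estimating the incidence, and the cost analysis is unaffected. The handling of unknown outcomes and chart-review patients is a real but smaller part of the point, since the numbers used to illustrate it are assumed. Defining small is a secondary clarification.

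**What to change.** No added patients are needed.

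1. Report 3-month septic arthritis incidence in each treatment group with a prespecified 95% interval. Exact Clopper-Pearson is a suitable default; whichever is chosen, name the method and sidedness before analysis.
2. State Aim 2 as estimation and tabulate the expected precision for up to 25 patients, as in Step 2. Treat below 10%, and below 5% in Hypothesis 3, as expectations, and call a threshold met only if the upper limit is below it.
3. Take prospective patients as the main estimate and show the result including chart-review patients separately. Report how many patients have an unknown 3-month outcome, and show results with them counted as no infection and as infection.
4. As a clarification, say whether Aim 2 concerns all non-operative arthrotomies or only small ones. If the latter, define small using the size in mm that is already collected.

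The cost is protocol wording, one interval per group and one sensitivity table, with no new data collection and no change to care. The downside is that the claim 25 patients can support becomes less favourable, and restricting to small arthrotomies or known outcomes may widen the interval further.
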